8. ADVERSE AND SERIOUS ADVERSE EVENTS ASSESSMENT

8.1 Definition of Adverse Events, Period of Observation, Recording of Adverse Events

According to the International Conference on Harmonization (ICH), an AE is "any untoward medical occurrence in a patient or clinical investigation subject administered a pharmaceutical product and which does not necessarily have a causal relationship with treatment. An AE can therefore be any unfavorable and unintended sign (including an abnormal laboratory finding), symptom, or disease temporally associated with the use of a medicinal (investigational) product, whether or not related to the medicinal (investigational) product" (ICH Guidance E6 [R2] 2016).

In this long-term outcome study in follow-up to Study SHP607-202, no investigational product is being administered; it is therefore a non-interventional study. However, it seeks information on whether prior administration of IMP in Study SHP607-202 impacts long-term outcomes.

For the purposes of this study only the following AEs will be collected:

- Specified targeted medical events (Section 8.1.4)
- AEs related to investigational product
- AEs leading to withdrawal from the study
- Serious AEs that occur during the study period or were previously present and worsen during the study period.

All AEs described above are collected from the time the informed consent is signed until the defined follow-up period stated in Section 3.2. Where possible, a diagnosis rather than a list of symptoms should be recorded. If a diagnosis has not been made, then each symptom should be listed individually. All AEs described above should be captured on the appropriate AE pages in the CRF and in source documents.

All AEs must be followed to closure (the subject's health has returned to his/her baseline status or all variables have returned to normal), regardless of whether the subject is still participating in the study. Closure indicates that an outcome is reached, stabilization achieved (the investigator does not expect any further improvement or worsening of the event), or the event is otherwise explained. When appropriate, medical tests and examinations are performed so that resolution of event(s) can be documented.

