8.1.4 Targeted Medical Events

If it is determined that any of the following targeted medical events have been experienced by a subject, they will be recorded as AEs or SAEs (refer to Section 8.2.3), as appropriate, regardless of relationship to prior investigational product (SHP607 as administered in Study SHP607-202):

- Intracranial hypertension
- Any abnormality of glucose metabolism (eg, hypoglycemia, hyperglycemia, and diabetes)
- Tonsillar hypertrophy (based on tonsil examination [part of the physical examination])
- Increased cardiac size

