8.2.3 Serious Adverse Event Definition

An SAE is any untoward clinical manifestation of signs, symptoms or outcomes (whether considered related to investigational product or not and at any dose:

- Results in death
- Is life-threatening. Note: The term “life-threatening” in the definition of “serious” refers to an event in which the subject was at risk of death at the time of the event; it does not refer to an event which hypothetically might have caused death if it was more severe.
- Requires inpatient hospitalization or prolongation of existing hospitalization. Note: Hospitalizations, which are the result of elective or previously scheduled surgery for pre-existing conditions, which have not worsened after initiation of treatment, should not be classified as SAEs.
- For example, an admission for a previously scheduled ventral hernia repair would not be classified as an SAE; however, complication(s) resulting from a hospitalization for an elective or previously scheduled surgery that meet(s) serious criteria must be reported as SAE(s).
- Results in persistent or significant disability/incapacity
- Is an important medical event. Note: Important medical events that may not result in death, be life-threatening, or require hospitalization may be considered an SAE when, based upon appropriate medical judgment, they may jeopardize the subject and may require medical or surgical intervention to prevent 1 of the outcomes listed in this definition. Examples of such medical events include:
 - Bronchospasm associated with anaphylaxis requiring intensive treatment in an emergency room or at home; blood dyscrasias or convulsions that do not result in inpatient hospitalization.
 - Reviewed and confirmed seroconversion for human immunodeficiency virus (HIV), hepatitis A virus (HAV), hepatitis B virus (HBV), hepatitis C virus (HCV), hepatitis E virus (HEV), or parvovirus B19 (B19V)

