7.1 Adverse Events

Adverse events will be coded using Medical Dictionary for Regulatory Activities (MedDRA) Version 24.0 or newer. For the purposes of this study only the following adverse events will be presented:

- Specified targeted medical events (Protocol Section 8.1.4)
- AEs related to investigational product (as administered in Study OHB-607-202)
- AEs leading to withdrawal from the study
- Serious AEs that occur during the study period or were previously present and worsen during the study period.

If it is determined that any of the following targeted medical events have been experienced by a subject, they will be recorded as AEs or SAEs, as appropriate, regardless of relationship to prior investigational product (as administered in Study OHB-607-202). The targeted medical events are considered as AEs of important potential risks and identified based on a list of pre-specified preferred terms (PTs):

- Intracranial hypertension: intracranial pressure increased, benign intracranial hypertension, fontanelle bulging, delayed fontanelle closure
- Any abnormality of glucose metabolism: hypoglycaemia, hypoglycaemia neonatal, blood glucose decreased
- Tonsillar hypertrophy (based on tonsil examination [part of the physical examination]): tonsillar hypertrophy, adenoidal hypertrophy, thymus enlargement, hypoacusis, snoring, ear tube insertion, tonsillectomy, adenoidectomy, sleep apnoea syndrome
- Increased cardiac size: cardiomegaly, cardiac hypertrophy, cardiac septal hypertrophy, ventricular hypertrophy, atrial hypertrophy, left ventricular hypertrophy, right ventricular hypertrophy, left atrial hypertrophy, right atrial hypertrophy, cardiomyopathy, cardiomyopathy neonatal, hypertrophic cardiomyopathy

An overall summary of the number of subjects as well as the number of events in each treatment group and overall will be presented, including the number and percentage of subjects with:

- Any AE (as specified in Protocol Section 8.1)
- Any SAE
- Any severe AE
- Any AE related to investigational product (IP) as administered in Study OHB-607-202

- Any SAE related to IP as administered in Study OHB-607-202
- Any severe AE related to IP as administered in Study OHB-607-202
- Any AE related to procedures performed in this study (SHP607-203)
- Any SAE related to procedures performed in this study (SHP607-203)
- Any severe AE related to procedures performed in this study (SHP607-203)
- Any AE leading to study discontinuation
- Any SAE leading to death

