The number and percentage of subjects reporting AEs, as well as the number of events (except for tables by the maximum severity), in each treatment group and overall will be tabulated, respectively, in following ways:

- By system organ class (SOC) and PT for all AEs
- By the maximum severity, SOC and PT for all AEs
- By SOC and PT for all AEs considered related to IP as administered in Study OHB-607-202
- By SOC and PT for all AEs considered related to study procedures
- By SOC and PT for all AEs leading to death
- By SOC and PT for all AEs leading to study discontinuation
- By SOC and PT for all SAEs
- By risk term, seriousness, and relationship to antecedent IP for AEs of important potential risks
- Most frequent AEs by PT (sorted by frequency, occurring in $\geq 5\%$ of subjects in any treatment arm)

In tables by severity or relationship, missing severity or missing relationship imputation will be applied, and handling of those missing cases are detailed in Section [9.2.2](#) and [9.2.3](#), respectively. If a subject had multiple occurrences of the same AEs, the subject will be counted only once per SOC and once per PT at the maximum severity. Handling of incomplete AE start/end dates is described in Section [9.2.1](#).

All AEs will be presented in a data listing. Separate data listings will be presented for AEs related to the antecedent IP, AEs related to study procedures, AEs leading to death, SAEs and AEs of important potential risks.

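### The SAP's tonsillar hypertrophy risk term counts eight preferred terms beyond the protocol's targeted event; their non-serious cases are collected essentially only in SHP607 children, so the row total can show a descriptive excess without a true effect

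*SAP*

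**What the plan says.** Protocol 8.1.4 lists four targeted medical events. The relevant one is "Tonsillar hypertrophy (based on tonsil examination [part of the physical examination". Targeted events are recorded "regardless of relationship to prior investigational product (SHP607 as administered in Study SHP607-202", so they are collected on the same rule in all arms.

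Protocol 8.1 restricts everything else: "For the purposes of this study only the following AEs will be collected". Besides targeted events, the list admits "AEs related to investigational product", events that lead to withdrawal, and "Serious AEs that occur during the study period or were previously present and worsen during the study period".

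SAP 7.1 repeats the protocol's label, including the reference to the tonsil examination, and then defines the risk term by nine PTs: "tonsillar hypertrophy, adenoidal hypertrophy, thymus enlargement, hypoacusis, snoring, ear tube insertion, tonsillectomy, adenoidectomy, sleep apnoea syndrome". The planned table is "By risk term, seriousness, and relationship to antecedent IP for AEs of important potential risks", shown by treatment group. Targeted events are a stated safety endpoint (SAP 3.2.4). SAP section 10 records only the dropped efficacy endpoints as a change from the protocol.

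**The concern.** Eight of the nine PTs are not named in Protocol 8.1.4. Several, such as hypoacusis, thymus enlargement and ear tube insertion, cannot be established by looking at the tonsils. What matters statistically is how such events reach the database. A snoring or hearing event that is neither serious nor a cause of withdrawal is within the collection rule only if the investigator relates it to SHP607. Standard-care children received no SHP607, so the same event in that arm goes unrecorded.

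The risk-term total would then set events collected in every arm beside events collected, when non-serious, essentially only in the SHP607 arms. Safety is all that this terminated study will report, and with so few children a handful of events can dominate a row.

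**Working it through.** **1. Collection route by type of event** (Protocol 8.1 and 8.1.4)

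| Event | Standard care | SHP607 arms |
|---|---|---|
| Tonsillar hypertrophy on examination | recorded | recorded |
| Other eight PTs, serious | recorded | recorded |
| Other eight PTs, leading to withdrawal | recorded | recorded |
| Other eight PTs, non-serious, no withdrawal | not recorded | recorded only if judged related |

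Only the last row differs by arm. It need not be small: the seriousness definition in Protocol 8.2.3 excludes "Hospitalizations, which are the result of elective or previously scheduled surgery for pre-existing conditions" that have not worsened, so some planned ear-tube, tonsil or adenoid admissions fall outside the serious route.

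**2. Can attribution differ in practice?** The parent study is open-label. Protocol 7.1 blinds only the assessors for BSID, KSPD, WPPSI, GMFM-88, spirometry and MRI; no blinding of adverse-event or causality assessment is stated. Protocol 8.1.2 sets a low threshold for calling an event related, although its guidance table is stricter. Protocol 1.2 reports adenotonsillar and hearing effects of rhIGF-1, which could prompt attribution.

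**3. Size.** The plan gives no figure to reproduce. Let p be the true incidence of the eight added PTs, equal in all arms; s the share that is serious; and r the probability that a non-serious case in an SHP607 child is judged related. Withdrawals are ignored; they act like a larger s.

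- Recorded rate in standard care: p × s
- Recorded rate with SHP607: p × (s + (1-s) × r)
- Ratio: 1 + (1-s) × r / s, which does not depend on p
- Difference: p × (1-s) × r

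| s | r = 0 | r = 0.10 | r = 0.25 | r = 0.50 |
|---|---|---|---|---|
| 0.50 | 1.00 | 1.10 | 1.25 | 1.50 |
| 0.25 | 1.00 | 1.30 | 1.75 | 2.50 |
| 0.10 | 1.00 | 1.90 | 3.25 | 5.50 |

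These ratios are for the added PTs alone. In the full row, tonsillar hypertrophy adds equally to both sides when there is no true effect and pulls the ratio towards 1.

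**4. Illustration in children.** SAP 3.1 puts enrolment below 10% of about 477. Since 0.10 × 477 = 47.7, that is at most 47. Arm sizes are not given. Assume 15 in standard care and 31 on SHP607 (both doses pooled for illustration), with p = 0.30 and s = r = 0.25.

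- Standard care: 0.30 × 0.25 = 0.075; 15 × 0.075 = 1.1 children
- SHP607: 0.30 × (0.25 + 0.75 × 0.25) = 0.131; 31 × 0.131 = 4.1 children
- Difference: 0.30 × 0.75 × 0.25 = 0.056, or 5.6 percentage points

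Summing exact binomial probabilities, the chance that SHP607 shows the higher proportion is 0.70, against 0.46 when r = 0.

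**5. After the fix.** If arms are compared only on events collected by the same rule, r drops out and the expected ratio is 1.00 at every p and s when there is no true effect.

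**The case against.** The strongest reply is that the suspect events can largely be found. By construction they are non-serious and related, and the risk-term table is split on exactly those two attributes. SAP 7.1 also plans tables by system organ class and PT for all, related and serious events, plus a listing of the events of important potential risk. A reader might infer that the two kinds of collection cannot be separated at all; the documents do not support that. What remains is that the row total mixes them, and the non-serious, related cell can also hold examination-based tonsillar hypertrophy. Nor does the split restore the unrelated, non-serious cases that were never collected.

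Other replies also have force:

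- SAP section 1 places table specifications in a separate document, so PT rows may already be planned there. The CRF instructions and Study Operations Manual are not supplied either; a wider term list given to sites would weaken the point.
- The grouping is biologically reasonable given Protocol 1.2. That is accepted; the difficulty is unequal collection.
- Arm-dependent collection comes from Protocol 8.1 and affects every non-targeted PT. True, but here such PTs are counted under the label of a targeted event.
- Exposure lasted under two months and this study starts at 12 months corrected age, so r may be low. At r = 0 the artefact vanishes.

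**Conclusion.** The point holds as a weakness of one table row. The SAP definition is wider than the protocol's targeted event, the widening is not declared, and the added non-serious cases are collected by an arm-dependent rule. Under equal true incidence the bias is either nil or towards an SHP607 excess. Its size rests wholly on assumed s and r: over the ranges shown, the ratio for the added PTs runs from 1.00 to 5.50.

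Three stronger conclusions are not supported. A reader might infer a false-positive finding, but no safety test is planned; the harm is a misleading descriptive imbalance. A reader might expect a large spurious gap, but the documents give no incidence, serious share or attribution rate. And a reader might treat adenoidal hypertrophy, tonsillectomy and adenoidectomy as part of the protocol-defined event; Protocol 8.1.4 does not name them, so they share the collection problem.

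**What to change.** In the SAP 7.1 table of adverse events of important potential risks:

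- Add a PT level under each risk term.
- Show the tonsillar hypertrophy PT alone as the protocol-defined row, comparable across arms in its collection rule.
- Show the other eight PTs in a separate row, compared between arms for serious events only. Footnote that non-serious cases not leading to withdrawal were collected only if judged related to SHP607.

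In SAP section 10, list the wider PT definition as a change from the protocol.

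The cost is one extra row level and a footnote in one table, plus an entry in section 10. No new data are needed, and the sponsor's broad grouping can still be shown.

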8.1.1 Severity Categorization

The severity of AEs must be recorded during the course of the event including the start and stop dates for each change in severity. An event that changes in severity should be captured as a new event.

The medical assessment of severity is determined by using the following definitions:

Mild: A type of AE that is usually transient and may require only minimal treatment or therapeutic intervention. The event does not generally interfere with usual activities of daily living.

Moderate: A type of AE that is usually alleviated with specific therapeutic intervention. The event interferes with usual activities of daily living, causing discomfort but poses no significant or permanent risk of harm to the research subject.

Severe: A type of AE that interrupts usual activities of daily living, or significantly affects clinical status, or may require intensive therapeutic intervention.

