9.8 Safety Analyses

Safety data will be analyzed for the Safety Population.

For safety analyses, baseline is defined as the first assessment in this study (Study SHP607-203). Treatment groups refer to the antecedent SHP607 dose groups (SHP607 at 250 µg/kg/day and SHP607 at 400 µg/kg/day), combined SHP607 dose groups, and standard neonatal care group.

The primary safety analysis will be based on:

- AEs reported during the study period of SHP607-203

The secondary safety analysis will be based on:

- Targeted medical events occurring during the period of Study SHP607-203.
- Fatal SAEs

Adverse events will be coded using the Medical Dictionary for Regulatory Activities. The number of events, incidence, and percentage of AEs will be calculated overall, by system organ class (SOC), by preferred term, and by treatment group. Adverse events will be further summarized by severity and relationship to prior investigational product. Adverse events related to investigational product, AEs leading to withdrawal, SAEs, and deaths will be similarly summarized/listed.

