3. INVESTIGATIONAL PLAN

3.1 Overall Study Design and Plan

This is a Phase 2b, multicenter, long-term outcomes study of subjects who were randomized in Study OHB-607-202 (previously known as SHP607-202) to either treatment (received OHB-607 [previously known as SHP607]) or control (received standard neonatal care) groups. Subjects are followed from 12 months CA through 5 years CA. Subjects are not excluded from participating in other clinical studies. No investigational product is administered in this study. Approximately 477 subjects who previously received OHB-607 or standard neonatal care in Study OHB-607-202 were planned to be enrolled in Study SHP607-203. Although all subjects randomized into the primary Study OHB-607-202 (approximately 477) are eligible to enroll in Study SHP607-203, the actual number of subjects enrolled would more closely approximate the number of subjects who complete Study OHB-607-202 (a total of approximately 382 subjects). The study designs are presented in Figure 1.

Figure 1 Study Design Flow Diagram

CA=corrected age; D=days; GA=gestational age; IV=intravenous; M=months; W=weeks; Y=years. Visits conducted at the study site are indicated in blue. Visits conducted by telephone are indicated in red.

In the Protocol Amendment 2 of Study OHB-607-202, the study design was updated to include a follow-up period until 24 months CA. As a result the sponsor decided to terminate Study SHP607-203.. The number of subjects enrolled in this study is less than 10% of the planned number, and few subjects completed the study (i.e. completed 5-year CA assessments). Thus, only sponsor-designated safety data will be analyzed and reported in this early-terminated study.

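### Does counting every severity change as a new adverse event make the event counts in SAP 7.1 misleading?

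*SAP*

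**What the plan says.** Protocol 8.1.1 sets the recording rule: "An event that changes in severity should be captured as a new event". It also asks for start and stop dates for each change of grade.

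Protocol 9.8 plans event counts: "The number of events, incidence, and percentage of AEs will be calculated overall", and then by SOC, preferred term and treatment group. SAP 7.1 follows this in its first table: "An overall summary of the number of subjects as well as the number of events in each treatment group". For the SOC and preferred-term tables it gives subjects "as well as the number of events (except for tables by the maximum severity"). Its one rule against double counting applies to children, not records: "the subject will be counted only once per SOC and once per PT at the maximum severity".

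What reaches these tables is narrow. Protocol 8.1 says "For the purposes of this study only the following AEs will be collected", and lists targeted medical events, product-related AEs, AEs leading to withdrawal, and serious AEs. Under Protocol 8.1.4, targeted events are recorded "as appropriate, regardless of relationship to prior investigational product".

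SAP Section 9 covers number formats and the imputation of dates, severity and causality. It has no rule for linking records. SAP Section 1 says the table specifications are in a separate document, which is not available here.

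**The concern.** Take the recording rule and the counting rule together. A child whose tonsillar hypertrophy is graded mild, then moderate, then mild again has one illness but three event records. The child appears once in the subject column and three times in the event column of the overall summary, the SOC/preferred-term table and the important-potential-risk table.

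SAP Section 6 drops the efficacy analyses, so the adverse-event tables are the main output, and the groups are small. One long, re-graded illness could visibly raise a group's event count. From the table alone, a reader could not tell more illness from more re-grading. The natural reaction is to ask for a rule that rejoins the segments before counting.

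**Working it through.** The plan states no figure to reproduce. The check is a counting argument followed by a list of what it reaches.

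**1. One illness.** The initial record plus one new record per grade change (Protocol 8.1.1) gives records = k + 1.

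| Grade changes k | Records | Children at that preferred term |
|---|---|---|
| 0 | 1 | 1 |
| 1 | 2 | 1 |
| 2 | 3 | 1 |
| 3 | 4 | 1 |

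**2. A whole table.** With E illnesses and a mean of m grade changes each, events = E(1 + m). Neither E nor m is in the documents. Assuming E = 20, the count is 22, 25, 30 or 40 for m = 0.1, 0.25, 0.5 or 1.0. At m = 0 it stays at 20.

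**3. Where k + 1 is only a ceiling.** Protocol 8.2.5 starts an SAE when serious criteria are met and lets it end when they no longer are; for hospitalizations it uses admission and discharge dates. Take a path of mild (not serious), severe (serious), moderate (not serious):

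- The all-AE table shows 3 records if all three are collected.
- The SAE table shows 1 if only the severe segment carries the flag.
- If the event is neither targeted nor product-related and did not lead to withdrawal, Protocol 8.1 may keep the two non-serious segments out of the database altogether.

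The discontinuation and death tables work the same way. The full k + 1 applies where every segment qualifies, as with targeted events.

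**4. What does not move.** Subject counts and percentages are protected by the once-per-SOC and once-per-term rule. The 5% cut-off for frequent AEs is defined on subjects. The maximum-severity tables carry no event counts. The listings show each record.

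**5. Study size.** SAP 3.1: "The number of subjects enrolled in this study is less than 10% of the planned number", which was approximately 477. 0.10 × 477 = 47.7, so at most 47 children. Spread evenly over three groups (an assumption), that is 47 / 3 ≈ 15.7 each.

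**6. What rejoining would do.** Suppose same-term records with touching or overlapping dates were merged, and a blank stop date were taken to run to the next record.

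- *Blank stop dates.* Mild hypoglycaemia at 18 months with no stop date, and a separate moderate episode at 4 years, would become one event across a gap of 48 − 18 = 30 months.
- *Partial dates.* Take a month after consent and before study end. Record 1 lacks its start and stop days in March; record 2 lacks its start day in March and stops on 20 April. SAP 9.2.1.1 sets both starts to 1 March, and SAP 9.2.1.2 sets the first stop to 31 March if stops are imputed. The records then overlap and merge, whether they are one illness or two.
- *Stop-date imputation.* SAP 9.2.1 foresees it only where a duration has to be calculated.

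**The case for a change.** The best argument for a change is that defining what is counted is the SAP's job. Protocol 9.3 assigns the definitions for the safety analysis to the SAP, and this SAP goes into fine detail on partial dates, missing grades and missing causality. A line on event counts would fit that level of detail and cost little. Some targeted events, such as tonsillar hypertrophy or increased cardiac size, can persist long enough to be re-graded, and Protocol 8.1 follows AEs to closure.

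Part of this stands. The SAP never states the unit next to the counts, and someone who sees only a table could misread it. The rest is weaker. SAP Section 1 ties the plan to Protocol Amendment 1, and that protocol says what a new event is, so calling the count inflated assumes that illnesses were the intended unit. The tonsil example is also unlikely. Scheduled examinations fall at 12 months, 24 months and 5 years CA, so three grades on schedule need all three visits, and SAP 3.1 says few children completed the 5-year assessments. Unscheduled findings could still produce it. Column labels and footnotes normally belong in the table specifications, which may already deal with this.

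**Conclusion.** No change to the plan is needed. The event columns count records as Protocol 8.1.1 defines them, up to k + 1 for a collected AE re-graded k times. The SAP applies that definition consistently. The tables are descriptive, no difference between groups is tested, and there is no reason to expect re-grading to favour one group. The total effect cannot be estimated and may be zero.

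A date-based merging rule would be a poor trade. It would swap a visible, traceable over-count of illnesses for the possible loss of real recurrences of targeted events. That runs against the cautious direction of SAP 9.2.2 and 9.2.3, which set missing severity to severe and missing causality to related. A table footnote saying that severity changes are counted separately would be a courtesy to readers; the conclusions do not depend on it.

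This rests on two assumptions: sites follow the Protocol 8.1.1 recording rule, and the unseen table specifications do not define events differently.
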